Visit Name	Screening	e 1	Cycl e 1 Day 15 Day 1 Da											day Safet y F-	End Post Treatme nt Follow- up	Surviv al F- up ⁴		
Days	-21 to -1	1	8 ±1	15 ±1	22 ±1	29 ±1	43 ±1	50 ±1	57 ±1	- ±3	-	- -0 +7	- ±7	- ±7	- ±7	- -0 +14	-	-
Tumor evaluation (CT scan/MRI/Bone scan)	-28 to -1	8-2 for	r imagir	weeks (+/- 1 week) for the first 9 months and every 12 weeks (+/- 1 week) thereafter, aging collection plan and Section 8.3.1. Upon the approval of amendment 4, the tumor assessments during the post-treatment efficacy period will be now optional and will be left at the discretion of the investigator.														
Chest X-ray		If clini	ically i	ndicate	ed													
ECG (Central)	At least 72 hours prior randomizati on	x					х				x							
ECG (Local)		s			s		s			On Day 1 of every 2 cycles after cycle 3								
Cardiac imaging (MRI/ECHO)	Х	If clini	linically indicated X															
Adverse Events			up to Day 150; non-suspected AE up to Day 150 or start of new post treatment anti-neoplastic medication, oner. See Appendix 1 (Safety follow-up diagram)															
Serious Adverse Events			to Day 150 and beyond; non-suspected SAE up to Day 150 or start of new post treatment anti-neoplastic medication, whichever is ndix 1 (Safety follow-up diagram)															

Novartis	Confidential	Page 86 of 185
Amended Protocol Version 04 (Clean)		Protocol No. CLAG525B2101

Period	Screening	Treat	ment								End of Treatment (EOT)	Follow	v-up³					
Visit Name	Screening	Cycl e 1 Day 1	Cycl e 1 Day 8	Cycl e 1 Day 15	Cycl e 2 Day 1	Cycl e 2 Day 8	Cycl e 3 Day 1	Cycl e 3 Day 8	e 3	Subseq. cycles Day 1	End of Treatment (EOT)	30 day Safet y F- up	60 day Safet y F- up	90 day Safet y F- up	120 day Safet y F- up	150 day Safet y F- up	End Post Treatme nt Follow- up	Surviv al F- up ⁴
Days	-21 to -1	1	8 ±1	15 ±1	22 ±1	29 ±1	43 ±1	50 ±1	57 ±1	- ±3	-	- -0 +7	- ±7	- ±7	- ±7	- -0 +14	-	-
Newly obtained tumor sample ²	Х																	
LAG525 infusion		Day 1	of eac	ch cycl	e (21 d	days) ι	ıntil EC	DΤ										

Period	Screening	Treat	ment								End of Treatment (EOT)	Follow	v-up³					
Visit Name	Screening	e 1	Cycl e 1 Day 8		e 2	e 2	e 3	e 3	Cycl e 3 Day 15	Subseq. cycles Day 1	End of Treatment (EOT)	30 day Safet y F- up	60 day Safet y F- up		120 day Safet y F- up	150 day Safet y F- up	End Post Treatme nt Follow- up	Surviv al F- up ⁴
Days	-21 to -1	1	8 ±1	15 ±1	22 ±1	29 ±1	43 ±1	50 ±1	57 ±1	- ±3	-	- -0 +7	- ±7	- ±7	- ±7	- -0 +14	-	-

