9.2.1 Follow up for safety evaluations

All participants must be followed for safety up to 150 days after the last dose of LAG525 and/or spartalizumab whichever was stopped last. After the 30-day onsite safety follow-up visit, participants will be followed (via telephone call or onsite visit if participant happens to be visiting the site) at 60 (+/- 7), 90 (+/-7), 120 (+/-7) and 150 (+14) days after the last dose of LAG525 and/or spartalizumab (whichever was stopped last). If carboplatin is stopped more than 150 days after LAG525 and/or spartalizumab, only the 30-day safety follow-up visit needs to be performed.

All safety assessments should be completed as per Table 8-1. However, if the participant begins post treatment antineoplastic medication before the 150-Day safety follow-up visit the collection of new SAEs and AEs unrelated to study medication will stop and thereafter only suspected AEs and suspected SAEs will continue to be collected up to Day 150. Suspected SAEs will continue to be collected beyond the 150-Day safety visit (see Section 16.1 Appendix 1). Data collected should be added to the appropriate eCRF pages. For female participants of child bearing potential, a pregnancy test will be performed at the time points listed in Table 8-1.

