- Dose not changed
- Dose Reduced (only for carboplatin)
- Drug interrupted/withdrawn
- 6. its outcome
 - a. not recovered/not resolved;
 - b. recovered/resolved;
 - c. recovered/resolved with sequelae;
 - d. fatal; or unknown

If the event worsens the event should be reported a second time in the CRF noting the start date when the event worsens in toxicity. For grade 3 and 4 adverse events only, if improvement to a lower grade is determined a new entry for this event should be reported in the CRF noting the start date when the event improved from having been Grade 3 or Grade 4.

Conditions that were already present at the time of informed consent should be recorded in medical history of the participant.

Adverse events (including lab abnormalities that constitute AEs) should be described using a diagnosis whenever possible, rather than individual underlying signs and symptoms.

Adverse event monitoring should be continued for at least:

- 150 days following the last dose of LAG525 and/or spartalizumab
- until the start of a new post treatment antineoplastic medication if sooner than the 150 days mentioned above. If a participant starts a post treatment antineoplastic therapy, then only adverse events suspected to be related to study treatment should be collected out to 150 days after discontinuation of LAG525 and/or spartalizumab
- 30 days after discontinuation of carboplatin if the participant continued carboplatin more than 150 days after the last dose of LAG525 and/or spartalizumab.

Once an adverse event is detected, it must be followed until its resolution or until it is judged to be permanent (e.g. Continuing at the end of the study), and assessment must be made at each visit (or more frequently, if necessary) of any changes in severity, the suspected relationship to treatment, the interventions required to treat it, and the outcome.

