10.1.3 SAE reporting

To ensure participant safety, every SAE, regardless of causality, occurring after the participant has provided informed consent must be reported to Novartis safety within 24 hours of learning of its occurrence and until:

- at least 150 days following the last dose of LAG525 and/or spartalizumab
- the start of a new post treatment antineoplastic medication if sooner than the 150 days mentioned above
- 30 days after discontinuation of carboplatin if the participant continued carboplatin more than 150 days after the last dose of LAG525 and/or spartalizumab.

If a participant starts a post treatment antineoplastic therapy, then only SAEs suspected to be related to study treatment should be collected out to 150 days after discontinuation of LAG525 and/or spartalizumab. SAEs suspected to be related to LAG525 and/or spartalizumab will continue to be collected beyond the 150-Day safety visit.

Detailed instructions regarding the submission process and requirements are to be found in the investigator folder provided to each site.

SAEs will be collected on all participants having signed an ICF and until reporting period is completed as described above. For participants who fail the screening, SAEs will be collected until the time the participant is deemed a Screen Failure.

All follow-up information for the SAE including information on complications, progression of the initial SAE and recurrent episodes must be reported as follow-up to the original episode within 24 hours of the investigator receiving the follow-up information. An SAE occurring at a different time interval or otherwise considered completely unrelated to a previously reported one must be reported separately as a new event.

If the SAE is not previously documented in the Investigator's Brochure or Package Insert (new occurrence) and is thought to be related to the study treatment, an oncology Chief Medical Office and Participant Safety (CMO & PS) Department associate may urgently require further information from the investigator for health authority reporting. Novartis may need to issue an Investigator Notification (IN) to inform all investigators involved in any study with the same study treatment that this SAE has been reported.

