Safety summaries (tables, figures) include only data from the on-treatment period with the exception of baseline data which will also be summarized where appropriate (e.g. change from baseline summaries). In addition, a separate summary for death including on treatment and post treatment deaths will be provided. In particular, summary tables for adverse events (AEs) will summarize only on-treatment events, with a start date during the on-treatment period (*treatment-emergent* AEs). However, all safety data (including those from the post-treatment period) will be listed and those collected during the pre-treatment and post-treatment period will be flagged.

Additional summaries will be displayed to report deaths, all AEs, AEs related to study treatment, all SAEs and SAEs related to study treatment collected up to 150 days after last administration of LAG525/spartalizumab or up to 30 days after the last dose of carboplatin whichever comes last..

Last contact date

The last contact date will be derived for subjects not known to have died at the analysis cut-off using the last complete date among the following:

Table 2-1 Last contact date data sources

Source data	Conditions
Date of Randomization	No Condition
Last contact date/last date subject was known to be alive from Survival Follow-up page	Subject status is reported to be alive, lost to follow-up or unknown
Start/End dates from further antineoplastic therapy	Non-missing medication/procedure term.
Start/End dates from study treatment pages	Non-missing dose. Doses of 0 are allowed.
End of treatment date from disposition page at end of treatment	No condition.
Tumor (RECIST / iRECIST) assessment date	Result is not missing
Verification for treatment beyond RECIST1.1 PD	At least one non missing parameter value
Laboratory/PK/IG collection dates	Was sample taken? = 'Yes'.
Vital signs date	At least one non-missing parameter value
Performance Status date	Non-missing performance status
Start/End dates of AE	Non-missing verbatim term

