2.9.1 Adverse events (AEs)

AE summaries will include all AEs occurring during on treatment period. Additional summaries will be displayed to report all AEs, AEs related to study treatment, all SAEs and SAEs related to study treatment collected up to 150 days after last administration of LAG525/spartalizumab or up to 30 days after the last dose of carboplatin whichever comes last. All AEs collected in the AE eCRF page will be listed along with the information collected on those AEs e.g. AE relationship to study drug, AE outcome etc. AEs with start date outside of on-treatment period will be flagged in the listings.

AEs will be summarized by number and percentage of subjects having at least one AE, having at least one AE in each primary system organ class (SOC) and for each preferred term (PT) using MedDRA coding. A subject with multiple occurrences of an AE will be counted only once in the respective AE category. A subject with multiple CTCAE grades for the same preferred term will be summarized under the maximum CTCAE grade recorded for the event. AE with missing CTCAE grade will be included in the 'All grades' column of the summary tables.

In AE summaries, the primary system organ class will be presented alphabetically and the preferred terms will be sorted within primary SOC in descending frequency. The sort order for the preferred term will be based on their frequency in the LAG525 + PDR001 + carboplatin arm, then on their frequency in the LAG525 + PDR001 arm and LAG525 + carboplatin arm.

The following adverse event summaries will be produced by treatment arm: overview of adverse events (number and % of subjects with any AE, treatment-related AE, SAE, treatment-related SAE, fatal SAE, treatment-related fatal SAE, AE leading to discontinuation, treatment-related AE leading to discontinuation, AE leading to dose adjustment/interruption, AE requiring additional therapy), AEs by SOC and PT, summarized by relationship (all AEs and AEs related to study treatment), seriousness (SAEs and non-SAEs), leading to treatment discontinuation, leading to dose adjustment/interruption, requiring additional therapy, requiring immunosuppressive medication, requiring systemic corticosteroid (> 10 mg of prednisone or equivalent), and leading to fatal outcome. Concomitant medications with immunosuppressive intent and systemic corticosteroids (>10 mg of prednisone or equivalent) will be programmatically flagged using a pre-specified list from the clinical team.

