A listing of all grouping levels down to the MedDRA preferred terms used to define each AESI will be generated.

Time to first occurrence of AESIs

Time to first occurrence of an AESI is defined as time from start of study treatment to the date of first occurrence of first event within an AESI, i.e. time in days is calculated as (start date of first occurrence of event) – (start of study treatment) +1.

In the absence of an event during the on-treatment period, the censoring date applied will be **the earliest** of the following dates:

- death date
- new anticancer antineoplastic therapy start date (not considering palliative radiotherapy),
- end date of on-treatment period
- data cut-off date
- withdrawal of informed consent date.

The corresponding censoring reason will be used: death, new anti cancer therapy, treatment discontinuation, ongoing at cut-off date or consent withdrawal.

The following AESIs will be considered for time to first occurrence analysis: Endocrinopathies, Colitis and Rash.

Failure curves (ascending Kaplan-Meier curves) will be constructed by treatment arm. Median together with 95% confidence interval as well as 25th percentile and 75th percentile will be presented for each treatment arm.

In addition, the median time to occurrence for the subset of subjects who experienced the event of interest will be calculated. Simple descriptive statistics, median, min and max as well as 25th percentile and 75th percentile, will be presented.

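### The day-150 all-cause AE, SAE and AESI tables run past the start of new antineoplastic therapy, after which only suspected events are collected, so all-cause incidence is under-counted for participants who switch

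*SAP*

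**What the plan says.** **Reporting.** SAP Section 2.1.1 states: "Additional summaries will be displayed to report deaths, all AEs, AEs related to study treatment, all SAEs and SAEs related to study treatment". Section 2.9.1 sets the window as events "collected up to 150 days after last administration of LAG525/spartalizumab or up to 30 days after the last dose of carboplatin whichever comes last". Section 2.9.1.1 applies the same window to all AESIs and all serious AESIs. AEs are summarised as the number and percentage of participants in the safety set. Protocol Section 12.5.2 describes the same additional AE and SAE summaries. None of these places mentions new anticancer therapy.

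**Collection.** Four places in the protocol change the rule once new therapy starts before day 150:

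- Section 9.2.1: "the collection of new SAEs and AEs unrelated to study medication will stop and thereafter only suspected AEs and suspected SAEs" continue to be collected.
- Section 10.1.1: AE monitoring runs "until the start of a new post treatment antineoplastic medication if sooner than the 150 days mentioned above"; after that, only suspected AEs are collected to day 150.
- Section 10.1.3: "then only SAEs suspected to be related to study treatment should be collected out to 150 days after discontinuation".
- Table 8-1, adverse event row: "non-suspected AE up to Day 150 or start of new post treatment anti-neoplastic medication".

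Protocol Section 6.2.2 prohibits no therapy during post-treatment follow-up, so switching inside the window is expected.

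**The concern.** The reporting window and the collection window differ, and they part at a date specific to each participant. After that date an event reaches an all-cause row only if an investigator in this open-label trial suspects study treatment. A late event attributed to the next therapy need not be recorded at all.

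The late window matters here because Protocol Sections 4.5.2 and 6.5.1.2.1 say that immune-related events may begin after treatment has stopped. A low all-cause SAE or AESI percentage to day 150 could be read as absence of events when part of it is absence of collection. If the arms differ in how many participants switch, or how soon, the comparison of these rows between arms is also affected.

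**Working it through.** The plan states no figure on this point, so there is none to reproduce. The check sets the two windows side by side and then illustrates the size under assumptions.

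**Step 1: windows.**

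| Period | All-cause table counts | Protocol collects |
|---|---|---|
| First dose to new therapy | All events | All events |
| New therapy to day 150 | All events, per the label | Suspected events only |

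The related-event tables match collection in both rows. The main AE tables stop 30 days after the last dose of any study treatment (SAP Section 2.1.1), so they have the gap only if new therapy starts within those 30 days.

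**Step 2: follow-up time without all-cause collection.** Let *q* be the share of participants who start new therapy and *t* the days from last dose to that start. Both are assumed. The share of the 150 post-dose days without collection of non-suspected events is *q* × (150 − *t*)/150.

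| *q* | *t* = 15 | *t* = 30 | *t* = 60 |
|---|---|---|---|
| 30% | 27% | 24% | 18% |
| 50% | 45% | 40% | 30% |
| 70% | 63% | 56% | 42% |

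For example, 0.5 × (150 − 30)/150 = 0.40. These are shares of the post-dose period only; the tables also include the on-treatment period.

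**Step 3: effect on a percentage.** Let *p* be the true 150-day probability of a non-suspected SAE after last dose, with constant hazard λ = −ln(1 − *p*)/150, independent of switching. Then observed = (1 − *q*)*p* + *q*(1 − exp(−λ*t*)). With *p* = 0.20 and *t* = 30, 1 − exp(−30λ) = 1 − 0.8^0.2 = 0.0436:

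- *q* = 30%: 0.7 × 0.20 + 0.3 × 0.0436 = 15.3%
- *q* = 50%: 0.5 × 0.20 + 0.5 × 0.0436 = 12.2%
- *q* = 70%: 0.3 × 0.20 + 0.7 × 0.0436 = 9.1%

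Over *t* = 15 to 60 the ranges are 14.7–16.6%, 11.1–14.3% and 7.5–12.0%.

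**Step 4: effect on the whole row.** As a stand-in for the rate up to last dose, take the 42.1% SAE rate of the earlier combination study (Protocol Section 1.1.3.3.2). The true total is 0.421 + 0.579 × 0.20 = 53.7%. Replacing 0.20 by the step 3 values at *t* = 30 gives 51.0%, 49.2% and 47.3%. The any-AE row starts at 98.9% in that study and barely moves: 99.1% true against 99.0–99.1% observed.

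**Step 5: arms.** The loss depends on *q* and *t* together, both measured from last dose. Two arms with equal *q* and *t* lose the same share, however fast they progressed on treatment. The ranking can even run against the switching share: 70% switching at day 60 loses 42%, while 50% switching at day 15 loses 45%.

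**The case against.** The strongest reply is that the consequence is limited. These are additional summaries. The main AE tables and the registry tables are restricted to the on-treatment period, the related-event tables are intact, and the cited collection rules set no stop at new therapy for recording deaths. Post-treatment anticancer therapy is already summarised by treatment group (SAP Section 2.4.2), and AEs starting outside the on-treatment period are flagged in listings. The SAP follows Protocol Section 12.5.2 and speaks only of events collected; it does not claim complete follow-up. All of this stands and bounds the point. It does not remove it: the word collected does not tell a reader that the rule changes at a different date for each participant, and these are the planned all-cause summaries of the 150-day safety period.

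A second reply is that simply cutting the all-cause tables at new therapy would create a new fault. Suspected late events would appear in the related tables but not in the all-cause ones, so related counts could exceed all-cause counts, and crude percentages over windows of different length would still reflect unequal follow-up. This is correct, and the fix below allows for it.

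A reader might also infer that the SAP has already adopted the needed rule, because its time-to-first-AESI analysis lists "new anticancer antineoplastic therapy start date" among the censoring dates. That rule applies only to participants with no event in the on-treatment period, whose end is itself a censoring date. It is not a precedent for the day-150 tables.

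**Conclusion.** The mismatch is explicit in the documents. As written, the day-150 all-cause AE, SAE and AESI tables under-count non-suspected events in participants who start new therapy inside the window, and may do so unequally by arm. The effect falls on the SAE, AESI and preferred-term rows; the any-AE row is near its ceiling.

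The size cannot be stated from the documents. The figures above rest on assumed switching shares and times, an assumed 20% event probability, a constant hazard, and independence of events and switching.

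Two stronger readings are not supported. A reader might infer that Arm 1 is under-counted most, because it was closed after more discontinuations for progressive disease. The window runs from last dose, and no share or timing of new therapy by arm is given, so that direction is plausible but not shown. A reader might also take the 85 of 88 participants off treatment at amendment 4 as a measure of switching. It shows only that nearly all had stopped study treatment.

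**What to change.** For all-cause AEs, SAEs and AESIs, end each participant's window at the earlier of two dates:

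- the planned window end, which is 150 days after last LAG525/spartalizumab or 30 days after last carboplatin, whichever is later;
- the start of new antineoplastic therapy, defined as in the protocol's collection rule.

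Report incidence over that window as an exposure-adjusted rate. By arm, show the number and timing of new-therapy starts and the observed window length.

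Keep the related-event tables to the full window. If the full-window all-cause tables are also kept, add a footnote that only suspected events are collected after new therapy. No suspected late event is then lost, and related counts do not exceed all-cause counts within the same window.

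The cost is one extra set of summaries and a date condition on data already collected. The change cannot recover events that were never recorded; it makes the reported window match the observed one.

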2.9.1.1 Adverse events of special interest / grouping of AEs

Adverse Events of Special Interest (AESI) consist of one or more well-defined safety events which are similar in nature and for which there is a specific clinical or safety interest in connection with the study compound. All definitions of AESI for LAG525 and spartalizumab will be stored in their respective Case Retrieval Strategy (CRS) sheet with clear versioning and reference to the MedDRA version used. If a CRS update is necessary, the final version needs to be available in a reasonable time ahead of the DBL. The CRS version will be included as a footnote of the AESI tables.

Data analysis of AESIs

An adverse event of special interest is a grouping of adverse events that are of scientific and medical concern specific to compound LAG525 or spartalizumab. These groupings are defined using MedDRA terms, SMQs (standardized MedDRA queries), HGLTs (high level group terms), HLT (high level terms) and PTs (preferred terms). Customized SMQs (Novartis MedDRA queries, NMQ) may also be used. A NMQ is a customized group of search terms which defines a medical concept for which there is no official SMQ available or the available SMQ does not completely fit the need. It may include a combination of single terms and/or an existing SMQ, narrow or broad.

AESI for LAG525 will be based on the most recent version of the dSPP and CRS for LAG525.

Based on the current version of the dSPP and spartalizumab CRS, AESI for spartalizumab are:

- Endocrinopathies
- Pneumonitis
- Colitis
- Hepatitis
- Nephritis
- Encephalitis
- Rash
- Infusion reaction
- Other immune disorders

For each specified AESI, number and percentage of subjects with at least one event of the AESI occurring during on treatment period will be summarized.

Summaries of these AESIs will be provided by treatment arm, (specifying grade, SAE, relationship, leading to treatment discontinuation, leading to dose adjustment/interruption, hospitalization, death, requiring immunosuppressive medication etc.). If sufficient number of events occurred, analysis of time to first occurrence will be applied.

Additional summaries will be provided to report all AESIs, AESIs related to study treatment, all serious AESIs and serious AESIs related to study treatment collected during the on-treatment period and up to 150 days after last administration of LAG525/spartalizumab or up to 30 days after the last dose of carboplatin whichever comes last.

A listing of all grouping levels down to the MedDRA preferred terms used to define each AESI will be generated.

Time to first occurrence of AESIs

Time to first occurrence of an AESI is defined as time from start of study treatment to the date of first occurrence of first event within an AESI, i.e. time in days is calculated as (start date of first occurrence of event) – (start of study treatment) +1.

In the absence of an event during the on-treatment period, the censoring date applied will be **the earliest** of the following dates:

- death date
- new anticancer antineoplastic therapy start date (not considering palliative radiotherapy),
- end date of on-treatment period
- data cut-off date
- withdrawal of informed consent date.

The corresponding censoring reason will be used: death, new anti cancer therapy, treatment discontinuation, ongoing at cut-off date or consent withdrawal.

The following AESIs will be considered for time to first occurrence analysis: Endocrinopathies, Colitis and Rash.

Failure curves (ascending Kaplan-Meier curves) will be constructed by treatment arm. Median together with 95% confidence interval as well as 25th percentile and 75th percentile will be presented for each treatment arm.

In addition, the median time to occurrence for the subset of subjects who experienced the event of interest will be calculated. Simple descriptive statistics, median, min and max as well as 25th percentile and 75th percentile, will be presented.

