In case time of assessment (e.g. pre-dose ECG) and time of treatment start is captured, the last available assessment before the treatment start date/time is used for baseline.

For safety parameters (e.g ECGs), where study requires multiple replicates per time point, the average of these measurements would be calculated for baseline (if not already available in the database).

In rare cases where multiple measurements meet the baseline definition, with no further flag or label that can identify the chronological order, then the following rule should be applied:

- If values are from central and local laboratories, the value from central assessment should be considered as baseline.
- If multiple values are from the same laboratory (local or central) or collected for ECGs or vital signs, then the value closest to normal should be considered as baseline.

If subjects have no value as defined above, the baseline result will be missing.

On-treatment assessment/event and observation periods

For adverse event reporting the overall observation period will be divided into three mutually exclusive segments:

1. **pre-treatment period:** from day of subject’s informed consent to the day before first administration of study treatment
2. **on-treatment period:** from date of first administration of study treatment to 30 days after date of last actual administration of any study treatment (including start and stop date)
3. **post-treatment period:** starting at day 31 after last administration of study treatment.

If dates are incomplete in a way that clear assignment to pre-, on-, post-treatment period cannot be made, then the respective data will be assigned to the on-treatment period. Refer to [Section 5.1.2](#) for imputation rules concerning AE start and stop dates.

For other safety data, the on-treatment period will start from the day after the date of first administration of study treatment, unless the time of assessment and time of treatment start is available on the day of study treatment start. For data where time of assessment (e.g. ECGs) and time of treatment start are captured, data collected on the day of first administration of study

treatment at a time before (after respectively) the time of first administration of study treatment will be considered on the pre-treatment period (on the on-treatment period respectively).

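### Time to first AESI: starting new anticancer therapy censors only those with no later on-treatment AESI, so the failure curves overstate incidence, on average slightly

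*SAP*

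**What the plan says.** SAP 2.9.1.1 defines the endpoint as "time from start of study treatment to the date of first occurrence of first event within an AESI". Nothing in that definition requires the AESI to come before new anticancer therapy. For censoring it says: "In the absence of an event during the on-treatment period, the censoring date applied will be" the earliest of five dates, namely death, new therapy, the end of the on-treatment period, data cut-off and consent withdrawal. The entry at issue reads "new anticancer antineoplastic therapy start date (not considering palliative radiotherapy", with the bracket then closed.

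SAP 2.1.1 runs the on-treatment period from first dose "to 30 days after date of last actual administration of any study treatment". New therapy does not shorten it.

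The output is described as "Failure curves (ascending Kaplan-Meier curves) will be constructed by treatment arm", with medians and quartiles. The scope is limited: "The following AESIs will be considered for time to first occurrence analysis: Endocrinopathies, Colitis and Rash". It is also conditional: "If sufficient number of events occurred, analysis of time to first occurrence will be applied".

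On data collection, Protocol 10.1.1 says that once a participant starts post-treatment antineoplastic therapy, "then only adverse events suspected to be related to study treatment should be collected", up to 150 days after LAG525 and/or spartalizumab is stopped. Protocol 9.2.1 says the same.

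**The concern.** Kaplan-Meier estimation needs the decision to keep or remove someone at a given time to rest on what is known by then. Here it rests on what happens next. Take two participants who start new therapy on the same day within 30 days of their last dose. If one has a rash a week later, that participant stays at risk up to the rash and counts. If the other has nothing, that participant is taken out at the switch. Later AESIs enter the numerator while event-free switchers leave the denominator, so the error always points upward. A cumulative-incidence estimator with the same rule would be biased in the same way, so this is separate from how death is handled.

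At stake are three sets of AESI curves by arm, under a secondary objective of characterising safety in each arm. Incidence would be too high, and time quantiles, where reached, too early.

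**Working it through.** **1. Which listed dates are affected.** Only new therapy.
- Nothing follows death.
- Data after cut-off are excluded (SAP 2.1), as are data after withdrawal of consent (SAP 2.2).
- The end of the on-treatment period bounds events and censoring alike.
- New therapy can fall before that end. It stops study treatment (Protocol 6.1.5), and no therapy is prohibited in post-treatment follow-up (Protocol 6.2.2). The exposed interval runs from the switch to 30 days after the last dose.

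**2. Contrast within the SAP.** For PFS and DOR, SAP 2.7.3 censors at the last adequate assessment when the event comes after new anticancer therapy. That condition applies whether or not an event follows, so it is consistent. The AESI rule lacks it.

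**3. Algebra of one step.** Let n be at risk, s of them switch together, and d of those s have an AESI inside the window. As written, the s − d event-free switchers are gone when the d events occur, so the step is d / (n − (s − d)). Following everyone to the end of the period gives d / n. Censoring everyone at the switch gives 0.
- n = 20, s = 12, d = 1: 1/(20 − 11) = 1/9 = 11.1%, against 1/20 = 5.0%, or 0.
- An arm of 34 with 2 early AESIs leaves 32 at risk. If 20 switch on day 70 and 2 of them have an AESI on day 80, the risk set is 32 − 18 = 14. As written: 1 − (32/34)(12/14) = 19.3%. Following everyone: 4/34 = 11.8%. Censoring everyone at the switch: 2/34 = 5.9%.

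These are constructed cases. They show that one or two events can move a small arm's curve noticeably.

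**4. Average size.** The documents state no figure for this analysis, so there is none to reproduce. Simulation with 600,000 participants per scenario assumed: constant AESI hazard giving 10, 20 or 30% at 6 months; median 100 days on treatment on a 21-day grid; 30, 60 or 90% starting new therapy 3 to 30 days after the last dose; deaths not modelled. None of these values comes from the documents. Estimated 6-month incidence:

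| True | As written, all post-switch AESIs recorded (30/60/90% switching) | As written, half recorded | Everyone censored at switch |
|---|---|---|---|
| 10% | 10.2 / 10.4 / 10.7% | 10.1 / 10.2 / 10.4% | 9.9–10.0% |
| 20% | 20.4 / 21.0 / 21.3% | 20.2 / 20.5 / 20.9% | 19.9–20.2% |
| 30% | 30.6 / 31.3 / 31.9% | 30.3 / 30.6 / 30.9% | 29.9–30.1% |

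The bias runs from 10.1 − 10.0 = 0.1 to 31.9 − 30.0 = 1.9 points. At 12 months, with 90% switching and full recording, it is 38.2 − 36.1 = 2.1 and 53.7 − 51.1 = 2.6 points. With no post-switch AESI recorded (run at true 20%, 60% switching), the rule as written and censoring everyone at the switch coincide, and the bias is zero.

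**5. The other consistent rule.** Ignoring new therapy and following everyone to the end of the period recovers the truth under full recording. With half recorded it falls low: 9.6–9.9%, 19.5–19.8% and 29.0–29.7%.

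**The case against.** The strongest case against acting is about size. To matter, an AESI must be the participant's first in its group, start after new therapy, fall within 30 days of the last dose, and be judged suspected, since only suspected events are collected after a switch. For an arm of 34 with equal hazard before and after switching, fewer than one such event is expected, and the sampling SD of the 6-month estimate is about 12 points at a hazard of 0.002 per day. The documents' own rates suggest nothing higher: Protocol 1.1.3.2.2 gives rash in 10% on single-agent spartalizumab (6.0% suspected), and Protocol 1.1.3.3.2 gives serious colitis in 4 of 356 on the combination. AESI groupings are broader than single terms, so these are only guides. The main AESI evidence, the frequency tables and the 150-day summaries, is untouched. All of this stands and limits the importance of the point. It does not make the rule valid.

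It could also be said that a programmer would take the earliest date for everyone anyway. The text does not say so, and followed literally it produces the flawed version.

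Three stronger readings are tempting but not supported:
- *The next therapy's own toxicity inflates the curves substantially.* If the hazard doubles after the switch and every such event is counted, simulation gives 35.4% against 31.0%. But events attributed to the next therapy would largely not be collected under Protocol 9.2.1 and 10.1.1.
- *Switching inside the 30 days is common, and Arm 1 is hit hardest.* SAP 1.1 reports more discontinuation for progression in Arm 1, but neither document says how often or how soon new therapy starts. A corner case with 70% switching 7 to 14 days after the last dose, hazard 0.002 per day and full recording gives 33.1% against 30.4%. That is an assumption, not a finding.
- *Median times are pushed upward.* Overstated incidence makes time quantiles earlier. At incidences such as those assumed here, the median and the 75th percentile would often not be reached.

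**Conclusion.** The rule is wrong as written. The direction, upward, follows from the text whenever any AESI is recorded between a switch and 30 days after the last dose. The average size is small: about 0.1 to 2 points at 6 months and up to about 2.6 at 12 months under the assumed ranges, 0.1 to 0.9 at 6 months if half of post-switch AESIs are recorded, and zero if none are. A single small arm can shift by more. These sizes depend on assumed AESI rates, time on treatment and switching.

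The analysis is descriptive, covers three AESIs and runs only if events suffice. A reader should not infer that the overall safety conclusions or the ORR decision are in doubt. The change is worth making because the estimate is invalid as specified and the correction costs almost nothing.

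**What to change.** Replace the opening condition in SAP 2.9.1.1 with a rule that applies to everyone, for example: *In this analysis an AESI counts as an event only if it starts on or before the earliest of the dates listed below; otherwise the participant is censored at that date, whether or not an AESI follows.*

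Keep AESIs that start after new therapy in the frequency tables and listings. Add a footnote to the curves that event counts may differ from the on-treatment AESI table.

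Cost: one sentence, one programming condition and one footnote. The downside is that a few AESIs starting after new therapy, including some suspected to be caused by study drug, leave the curves.

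Dropping new therapy from the list would also be consistent and would keep the event window aligned with the AESI table. However, it treats partly observed time as fully observed, and step 5 shows it then underestimates incidence.
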